### ***C. Withdrawal Criteria***

Patients will be free to withdraw from the study at any time.

### ***D. Intervention***

Patients will be given a tablet computer. Explanation of the trial, followed by a “agree” or “disagree” option will be presented. Those who continue will be assumed to have provided consent. If they select, “continue,” the system then will randomize them. Patients will be randomized by computer 1:1 to either the treatment group or the control group at PACE clinic. Patients will be stratified according to chronic pain (chronic pain syndrome present). Randomization will be computer generated with random permuted block size 2 and 4, and allocation will be concealed. Caregivers and evaluators will be all masked to group allocation. The treatment group will receive a formal education presentation detailing realistic postoperative pain expectations and goals, the benefits and risks of opioids, wise use of opioids (lowest effective dose for the shortest time necessary), and non-opioid alternatives. In general form, it will be similar to the education video developed and used by Syed et al. The control group will receive preoperative education regarding surgery per PACE clinic protocol on general preoperative education. Each educational tool consists of a ≈4-minute-long video that will be presented on a tablet computer during their preoperative visit and again shortly before surgery.

### ***E. Protocol***

Patients must meet all inclusion and exclusion criteria to be eligible for the study. After eligibility is confirmed, an investigator will randomize patients to “analgesic Version 6.0, January 4, 2023

education" or "general perioperative education". During the preoperative PACE visit, patients will be given a CCF-approved tablet computer that contains a brief introduction for the study, and "analgesic education" or "general perioperative education" videos which each of them takes 4 minutes.

An unblinded research fellow will see participating patients before in the morning of their planned procedures and ask them to again watch the original "analgesic education" or "general perioperative education" reinforcement. Anesthetic management will follow pre-established clinical and institutional guidelines, but not be otherwise be controlled. Premedication, type of anesthesia, regional blocks, and intraoperative and postoperative opioid management will all be left to the discretion of the attending anesthesiologist.

In the PACU and postoperative periods, patients will be managed at the discretion of the primary care team and anesthesiologist. Postoperative opioids will be provided per clinical routine. Administration of regional anesthesia (including neuraxial and nerve blocks) preoperatively or postoperatively will be at the discretion of the clinicians who will adjust analgesic management as necessary.

#### ***F. Measurements***

Demographics and comorbidities (*Table 1*) will be obtained from electronic medical reports. Blinded clinical evaluators will query patients for outcomes. Clinicians including nurses will be blinded to study and will be required to perform routine clinical management after surgery. Patients will be followed for outcomes daily for up to 72 hours after surgery. Any opioids prescriptions at discharge will be at the discretion of the primary care team. Long-term outcomes including modified brief pain inventory scores and the use of analgesics will be collected 90 days after surgery by telephone.

*Primary outcome* is opioid consumption during the initial 72 hours after surgery, will be collected from electronic medical records if discharged will be approached by phone and converted to morphine equivalent. Differences in morphine equivalents of 20% or more will be interpreted as clinically meaningful.

*Secondary Aim 1*; satisfaction with post-operative pain management will be evaluated using a 0-10 Likert scale (where 0 means not satisfied at all and 10 means

completely satisfied) on the third day after surgery by phone by blinded clinical evaluators. Difference of 2 points in satisfaction will be accepted as clinically meaningful difference.

**Secondary Aim 2;** pain scores will be obtained from electronic medical records which are recorded by nursing, in PACU it is every 15 minutes and in ward every 4 hours while hospitalized. Difference of 1.2 points in pain scores will be accepted as clinically meaningful difference.

**Exploratory Aim 1;** composite of opioid related side effects and the antiemetic use will be obtained from nursing and medication notes from electronic medical records.

**Exploratory Aim 2;** analgesic use will be obtained from the Ohio prescription

Sex
Age (years)
Ethnicity
Height (cm)
Weight (kg)
BMI
ASA status
Surgery Type
Smoking status (current, former, never)
Medical History : Pulmonary disease, Kidney disease, Hypertension, Diabetes Mellitus, Neurologic disease, Coronary Artery Disease, Myocardial infarction, Chronic pain conditions, illegal drug usage, alcohol abuse, previous surgery or stent placement and medication usage

registry at 3 months.

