#### ***Secondary Aims***

*Secondary Aim 1:* To assess whether patients assigned to analgesic education (versus standard/generic) have better patient satisfaction with post-operative pain management.

Hypothesis: Patients assigned to analgesic education are more satisfied with pain management after surgery as measured on a 0-10 Likert scale (where 0 means not satisfied at all and 10 means completely satisfied) on the third day after surgery.

*Secondary Aim 2:* To assess the effect of analgesic education on postoperative pain during the first 72 post-operative hours or until discharge (whichever is earlier)

Hypothesis. Patients assigned to analgesic education have lower time weighted average pain scores during the first 72 post-operative hours or until discharge (whichever is earlier).

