### ***B. Setting and Population***

#### **i. Inclusion criteria**

1. Modified informed consent;
2. Adults  $\geq 18$  years;
3. American Society of Anaesthesiologists physical status 1-4;
4. Scheduled for hip arthroplasty, laparoscopy assisted abdominal surgery;
5. In-person visit the PACE clinic;

6. Anticipated at least 24 hours stay after surgery;
7. Reasonable English fluency.

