#### **Primary Analysis**

The effect of pre-operative patient education on cumulative opioid consumption (morphine equivalents) during first 72 postoperative hours will be assessed by using a t-test on the log transformed opioid consumption. Linear regression will be used to adjust for imbalance if necessary. The 95% CI for the ratio of geometric means (intervention/placebo) between the two groups will be reported.

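### The primary 72-hour opioid total mixes charted doses with patients' phone reports after discharge, and the planned analysis cannot separate lower use from lower reporting

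*Combined protocol and SAP*

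**What the plan says.** All references are to the combined protocol and SAP.

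- **Outcome and source.** F. Measurements defines the primary outcome as "opioid consumption during the initial 72 hours after surgery". The data "will be collected from electronic medical records if discharged will be approached by phone and converted to morphine equivalent". No diary, pill count or other check of the phone-reported doses is described. The state prescription registry is mentioned only for analgesic use at 3 months.
- **Length of stay.** The inclusion criteria require "Anticipated at least 24 hours stay after surgery", which is a minimum and an expectation.
- **Content of the videos.** D. Intervention says the education presentation covers, among other topics, "wise use of opioids (lowest effective dose for the shortest time necessary"). The control group gets general preoperative education. Each video lasts about 4 minutes and is shown twice.
- **Masking.** D. Intervention states: "Caregivers and evaluators will be all masked to group allocation". F. Measurements adds: "Blinded clinical evaluators will query patients for outcomes". Patients are not listed as masked.
- **Analysis.** Under Primary Analysis, the effect on the 72-hour total "will be assessed by using a t-test on the log transformed opioid consumption", with linear regression if baseline imbalance calls for it. No analysis by data source is given.
- **Contrast.** Secondary Aim 2 measures pain "during the first 72 post-operative hours or until discharge (whichever is earlier"), from nurse-recorded scores. The opioid outcome has no version that stops at discharge or uses chart data alone.

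**The concern.** Masked evaluators limit interviewer bias. They do not affect what a patient chooses to say. A patient who has twice been advised to use little opioid for a short time may report less than was taken. That pressure comes from the content of the video, so it can act even if the patient does not know the hypothesis. No matching message is described for the control arm.

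If such an effect exists, it runs in the direction of the hypothesis. It also does not shrink with sample size: raising enrolment to 1060 reduces the standard error and leaves the bias where it is. A significant geometric mean ratio could then reflect reporting, use, or both, and nothing in the planned output would let a reader tell which.

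**Working it through.** **1. How much of the window can be self-reported.** Discharge at the 24-hour minimum leaves 72 - 24 = 48 hours, or 48/72 = 67% of the window. This is the upper end, and a share of time. The documents give no length of stay and no share of dose taken at home.

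**2. The plan's own figures.** Log-scale SD = sqrt(ln(1 + CV²)); n per arm = 2(1.960 + 1.282)² SD² / (ln 0.80)², two-sided 0.05, 90% power.

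- CV 1.00: SD 0.833; 293 per arm, or 294 with the noncentral t, total 588. The plan says 588.
- Group-sequential inflation: 672/588 = 1.143.
- CV 1.32: SD 1.004; 426 per arm, total 852; 852 × 1.143 = 974. The plan says 974.
- CV 1.30: SD 0.995; 418 per arm, total 836; 836 × 1.143 / 0.9 = 1062. The plan says 1060.

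The sample size arithmetic reproduces. It matters here only because it sets the standard error.

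**3. Standard error.** 1060 × 0.9 = 954 evaluable, 477 per arm. SE of the log ratio = 0.995 × sqrt(4/954) = 0.0644. A ratio of about exp(-1.96 × 0.0644) = 0.881 or lower is significant at 0.05. At the planned final boundary of 0.044, taken as two-sided, the limit is 0.878.

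**4. False-positive rate with no true effect.** Let q be the proportion discharged before 72 hours, f the share of their 72-hour dose taken at home, and u the extra under-reporting in the education arm. None of the three is in the documents, so all values are assumptions. The apparent ratio is r = (1 - f·u)^q, and the two-sided rejection rate is Φ(-1.96 - ln r/SE) + Φ(-1.96 + ln r/SE). With q = 1, f is the self-reported share of all use.

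| q | f | u | Apparent ratio | Two-sided rate |
|---|---|---|---|---|
| 0.5 | 0.2 | 0.1 | 0.990 | 5.3% |
| 1 | 0.2 | 0.1 | 0.980 | 6.1% |
| 0.5 | 0.2 | 0.2 | 0.980 | 6.2% |
| 0.5 | 0.4 | 0.2 | 0.959 | 9.9% |
| 1 | 0.2 | 0.2 | 0.960 | 9.7% |
| 1 | 0.3 | 0.2 | 0.940 | 16.1% |
| 1 | 0.4 | 0.2 | 0.920 | 25.3% |

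Worked case, last row: ln 0.920 = -0.0834; -0.0834/0.0644 = -1.294; Φ(-0.666) = 0.253, and the other tail is negligible. At the 0.044 boundary the three rows with q = 1 and u = 0.2 become 8.8%, 14.8% and 23.6%.

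The model assumes proportional under-reporting and unchanged variance, and looks at the final analysis alone.

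**5. Power of a 24-hour chart analysis.** With 477 per arm and the noncentral t, power for a ratio of 0.80 is 93% at log SD 0.995 and 82% at log SD 1.2. The 24-hour SD is an assumption, and so is the full 0.80 effect arising within 24 hours.

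**The case against.** Several points on the other side are sound.

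- **Size.** Every input to the bias model is assumed. With modest values the error rate is close to nominal. A reader might take 25% as the expected error rate. The documents do not support that: it needs 40% of all opioid use across the arm to be self-reported, so most patients would have to go home early.
- **Time is not dose.** A reader might infer from the 67% figure that two thirds of the outcome is self-reported. It describes hours in an extreme case, and no discharge data are given.
- **Clinical threshold.** F. Measurements treats differences of 20% or more as clinically meaningful. The spurious ratios in the table lie between 0.92 and 0.99. In this model bias alone reaches 0.80 only when f·u = 0.20 across the whole arm, for example 0.4 × 0.5. That limits what a spurious result could be claimed to show. It does not prevent false significance.
- **Mitigation.** Attention is matched by a control video shown equally often, evaluators are masked, and follow-up is daily, so recall is short. The education video also covers the benefits of opioids, so it is too strong to say that it urges patients to take as little as possible.

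What stands is that none of these features addresses a one-sided reporting pressure, and the plan has no output that would show whether it occurred.

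**Conclusion.** The point holds as a weakness in design and reporting, of unknown size. Phone report after discharge is combined with chart data, patients are not listed as masked, one arm alone is described as receiving advice on restraint, and only the combined total is analysed. Differential under-reporting could bias the ratio towards benefit.

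Under the assumed values the two-sided false-positive rate lies between about 5-6% and 25%. About 10% corresponds to half of patients discharged early, 40% of their dose at home and 20% under-reporting. The documents do not show that under-reporting will occur, and they do not support the inference that a positive result would be false. They show only that the planned analysis could not tell the two explanations apart.

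**What to change.** Keep the primary analysis unchanged and add the following to the SAP.

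1. A supportive analysis with the same log-scale model on chart-recorded opioid in the first 24 hours after surgery, a common window when most patients are expected to be inpatients. This is better than chart data up to discharge, because discharge time follows randomisation and the education could affect it.
2. By arm, the proportion discharged before 72 hours and the share of the 72-hour total that came from phone report.
3. The 24-hour ratio with its 95% CI beside the primary ratio. If the effect is confined to the phone-reported part, describe the result as possibly dependent on self-report.

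Do not use a rule that accepts the primary result whenever the 24-hour ratio merely lies on the same side of 1. Both outcomes come from the same patients, so chance imbalance moves them together. In a simulation with no true effect, 20% under-reporting and 20-40% of all use self-reported, the 24-hour ratio was below 1 in 76-84% of the spuriously significant results at an assumed correlation of 0.5, and in 93-99% at 0.8. Such a rule would pass most of the errors it is meant to catch.

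The cost is SAP wording, one more model and two descriptive summaries on data already collected, provided phone-reported doses can be told apart from charted doses in the dataset. The 24-hour window cannot show true effects that arise after discharge, so it is supportive only.

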**Table 1: Baseline and demographic characteristics**

### ***G. Statistical Plan and Sample size estimation***

Analyses will be modified intent-to-treat, including all randomized patients who received treatment (i.e., patients randomized but not receiving treatment will not be included in the analyses). The treatment groups will be compared on baseline characteristics using absolute standardized difference (ASD), defined roughly as the absolute difference in means divided by the pooled standard deviation. Imbalance will be defined as an ASD of greater than 0.10. All the analyses will be adjusted for imbalanced baseline characteristics. The confidence level for all analyses is set at 95% ( $p < 0.05$ )

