#### ***Primary Aim***

To assess whether patients assigned to an analgesic education video have reduced short-term postoperative opioid consumption compared to those randomized to a generic education video.

Hypothesis: Our primary hypothesis is that patients assigned to analgesic education use less opioid between the end of surgery and the third postoperative morning (cumulative mg morphine equivalents).

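### The analysis set drops randomised patients who did not receive the video, although the primary aim compares patients as assigned; the bias risk is probably small and cheap to remove

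*Combined protocol and SAP*

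**What the plan says.** Section G (Statistical Plan and Sample size estimation) restricts the analyses to those who were both randomised and treated: "patients randomized but not receiving treatment will not be included in the analyses". No endpoint is exempt, no assignment-based analysis is planned beside it, and receiving treatment is not defined.

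The Primary Aim is worded by assignment. It asks whether "patients assigned to an analgesic education video have reduced short-term postoperative opioid consumption compared to those randomized to a generic education video". The outcome window runs "between the end of surgery and the third postoperative morning".

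Section D (Intervention) gives the order of events: "Patients will be randomized by computer 1:1 to either the treatment group or the control group at PACE clinic". A video of about four minutes, in either arm, is then "presented on a tablet computer during their preoperative visit and again shortly before surgery". On the second showing, section E (Protocol) says: "An unblinded research fellow will see participating patients before in the morning of their planned procedures". The fellow will "ask them to again watch the original" video, which section E describes as reinforcement.

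Section F (Measurements) says that the primary outcome "will be collected from electronic medical records if discharged will be approached by phone and converted to morphine equivalent".

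**The concern.** The planned set answers a question about patients who received a video, while the aim asks about patients assigned to one. The mismatch exists whatever the rate of non-receipt turns out to be.

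Receipt is also an event after randomisation, so conditioning on it gives up part of what randomisation protects in the primary comparison. A usual reason for a modified set is that there is no outcome to analyse. That reason does not apply to a patient who skipped the video, had surgery and stayed in follow-up, because neither the records nor the phone contact depends on viewing.

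The missing definition adds to the problem. If one showing counts as receipt, few patients should be affected. If both are required, more could be, and the second showing is run by someone who knows the assignment.

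**Working it through.** **1. The plan's own figures.** Inputs from section H (Sample Size Calculations): ratio 0.80, 90% power, significance level 0.05 (sidedness not stated; two-sided reproduces the figures), CV 1.00 at first and 1.30 on re-estimation, 10% drop-out, totals of 588, 672 and 1060. On the log scale the effect is d = −ln(0.80) = 0.2231 and the SD is s = √ln(1 + CV²).

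- CV 1.00: s = 0.833. A two-sample t-test needs 588 in total, as stated.
- Group-sequential inflation implied by the plan: 672/588 = 1.143.
- CV 1.30: s² = ln(2.69) = 0.9895, s = 0.9948. The t-test needs 838; 838 × 1.143 = 958; 958/0.9 ≈ 1065, close to the stated 1060.

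The sample size is therefore not in dispute and can serve as the base. Evaluable patients: 1060 × 0.9 = 954, or 477 per arm.

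**2. When the exclusion biases the ratio.** Let a fraction e of one arm be dropped, and let the dropped patients' mean log opioid use lie k SDs from that arm's mean. The mean of those kept then moves by

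shift = e/(1 − e) × k × s.

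If k = 0 the shift is zero for any e, so unequal numbers alone do no harm. If e and k are the same in both arms, the two shifts cancel. Bias needs both conditions: the excluded differ from the kept, and the exclusions differ between arms in number or type.

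**3. Size of the bias.** The documents give neither e nor k, so both are assumed: k = 0.5, one arm only affected, true ratio 1.00. SE = √[s²(1/(477(1 − e)) + 1/477)]; x = shift/SE; type I error of a fixed two-sided 5% test = Φ(−1.96 + x) + Φ(−1.96 − x). The interim looks are ignored.

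| e, one arm only | shift | x | apparent ratio | type I error |
|---|---|---|---|---|
| 1% | 0.0050 | 0.078 | 0.995 (or 1.005) | 5.1% |
| 2% | 0.0102 | 0.157 | 0.990 (or 1.010) | 5.3% |
| 5% | 0.0262 | 0.401 | 0.974 (or 1.027) | 6.9% |

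The values in brackets apply if the dropped patients lie on the other side of the mean. With 5% dropped from one arm and 2.5% from the other, and the same k, the net shift is (0.05/0.95 − 0.025/0.975) × 0.5 × 0.9948 = 0.0134. The ratio is then 0.987 and type I error 5.5%.

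**4. Cost of keeping these patients.** Suppose a fraction f in each arm never views the video and gets no effect from it. The fixed-design equivalent of 954 is 954 × 588/672 = 834.75, and power = Φ(d/√(4s²/n) − 1.96), which gives 90.0% at f = 0. Keeping them replaces d by d(1 − f); dropping them replaces n by n(1 − f).

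| f | ratio if kept | power, kept | power, dropped | difference (points) |
|---|---|---|---|---|
| 1% | 0.802 | 89.4% | 89.7% | 0.3 |
| 2% | 0.804 | 88.8% | 89.4% | 0.6 |
| 5% | 0.809 | 86.8% | 88.5% | 1.6 |

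Differences are taken before rounding.

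**The case against.** The strongest reply is that almost nobody will be excluded. The tablet takes agreement, randomises, and the video follows at the same visit. Both arms see a video of the same length by the same procedure, so non-receipt should be rare and similar in the two arms. The rule is also disclosed and pre-specified. This stands as to size: the 1% and 2% rows are negligible, and the 5% row needs non-receipt in one arm only plus a half-SD difference. It does not remove the mismatch with the aim, and if few patients are involved the remedy is nearly free.

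A second reply is that the outcome will not exist for every excluded patient. This is correct. A cancelled operation leaves no postoperative opioid use. Section C allows withdrawal at any time, and someone who declines the video may also decline the phone call. Section E, unlike section D, places randomisation before its mention of the tablet introduction, so a patient who then presses disagree might already be randomised. These cases limit the remedy to consented patients who had surgery and have data. That set is itself conditional on events after randomisation, but without surgery there is no outcome window, and nothing in the documents links cancellation to the assigned video.

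A third reply is timing. The current version follows three interim looks, so changing the primary set is a substantive late amendment. That calls for documentation and for reporting both sets. It does not justify leaving the primary analysis at odds with the aim.

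A reader might go further and infer that the unblinded fellow's role makes exclusions selective, or that the rule favours the analgesic video. The documents do not support this. They report no difference in non-receipt, and the natural reading is that the clinic showing is the treatment.

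**Conclusion.** The point holds in limited form. The planned set does not match the assignment-based aim, and it excludes patients for an event after randomisation even where their 72-hour opioid use can be obtained. Whether this biases the ratio depends on the two conditions in step 2 of the working. No direction is claimed.

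The effect is probably small. At an assumed 1% to 2% dropped from one arm only, half an SD apart, the ratio moves by 1% or less and type I error reaches at most 5.3%. The 6.9% figure is the result of a less favourable assumption and should not be read as an expected error rate. The 10% drop-out allowance protects precision and does nothing about selection. The change is worth making because it is cheap and settles the question, and not because the trial is invalid without it.

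**What to change.** In section G, define the primary set as all consented, randomised patients who had surgery and have outcome data, analysed by assigned video whether or not they viewed it. Keep the current set as a sensitivity analysis, with receipt defined as at least one viewing of the assigned video. At the final analysis, apply the assignment-based set to all patients, including those who contributed to the interim looks. Document the change and its date before unblinding, state that the plan in force at the three looks specified the treated-only set, and report both results.

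The cost is an amended definition in section G, one further analysis and no new type of data. There are two downsides. Dilution costs 0.3 to 1.6 points of power if an assumed 1% to 5% never view, and the final set may differ slightly from the set used at the interim looks.

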#### **Secondary Analysis**

The effect of the intervention on patient quality satisfaction scores assessed on the third post-operative day will be determined by using a t-test or linear regression adjusting for imbalanced covariates as appropriate. If the distribution of patient satisfaction scores is skewed, we will use Wilcoxon rank-sum test or log-transformed scores to assess the effect.

The effect on time-weighted average pain scores during the first 72 post-operative hours will be assessed in a manner similar to that for patient satisfaction scores.

Adjusting for multiple testing using the Bonferroni correction, the secondary analyses will be carried out at the 97.5% confidence level (i.e.  $p < 0.05/2$ ).

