## **Interim Analysis**

Three interim analyses will be conducted at 25%, 50% and 75% of the planned enrollment to assess efficacy utility using a group sequential design with a gamma spending function (Gamma = -4 for efficacy and Gamma = -1 for futility) with non-binding efficacy and futility boundaries. The probability of crossing either the efficacy or futility boundary at the first, second and third interim analysis will be 9%, 40% and 78% respectively if the alternative hypothesis is true.

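### Covariates enter the primary model only through chance imbalance (ASD above 0.10), so the randomisation stratum is in effect never adjusted for and surgery type only occasionally. This costs precision, not validity.

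*Combined protocol and SAP*

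**What the plan says.** - **Randomisation (D. Intervention).** Allocation is 1:1 with one stratification factor: "Patients will be stratified according to chronic pain (chronic pain syndrome present". The method is: "Randomization will be computer generated with random permuted block size 2 and 4, and allocation will be concealed".
- **Population (B. Setting and Population, Inclusion criteria).** Two kinds of surgery are enrolled: "Scheduled for hip arthroplasty, laparoscopy assisted abdominal surgery". Surgery type is not a stratification factor.
- **Covariate rule (G. Statistical Plan).** "Imbalance will be defined as an ASD of greater than 0.10". The next sentence is "All the analyses will be adjusted for imbalanced baseline characteristics".
- **Primary Analysis.** The default is a two-group t-test on log morphine equivalents, followed by: "Linear regression will be used to adjust for imbalance if necessary". Secondary Analysis has the same structure: "t-test or linear regression adjusting for imbalanced covariates as appropriate".
- **Candidates.** Table 1 lists both surgery type and chronic pain conditions, so both are eligible under the rule. No section makes either a fixed model term.
- **Interim Analysis.** "Three interim analyses will be conducted at 25%, 50% and 75% of the planned enrollment". The section does not say whether covariate selection is repeated at each look.

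**The concern.** The rule selects covariates by how unequal the arms happen to be, not by how well the covariates predict opioid use. Stratified blocking removes inequality in the one factor that the sponsor chose to stratify on, so the rule screens that factor out of the model. Surgery type is a natural candidate predictor of opioid use, yet it is left to chance.

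If either factor is prognostic, the unadjusted standard error is too wide. The between-arm comparison gains from stratification, but the analysis does not credit that gain. Three things are at stake:

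- **Precision.** Some that is available at no cost is not used.
- **Prespecification.** The rule is written down, but the model it produces is unknown until the baseline data are in.
- **Consistency across looks.** If the rule is re-applied at each interim analysis, the covariate set can change from one look to the next.

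**Working it through.** **1. The plan's own figure.** Log SD = sqrt(ln(1 + CV²)), effect = |ln 0.80| = 0.2231, two-sided 0.05, 90% power, n per arm = 2(1.960 + 1.282)² × log variance / effect².

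- CV 1.00: log variance ln 2 = 0.6931, total 585 by the normal approximation and 588 with the t refinement. H. Sample Size Calculations states 588.
- CV 1.30: log variance ln(2.69) = 0.9895, 418 per arm, total 838 with the t refinement. Multiplying by 672/588 for the interim looks and dividing by 0.9 for dropout gives 1064. Third interim analysis re-assessment states 1060.

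The trial is therefore sized for an unadjusted comparison. With 1060 × 0.9 = 954 evaluable (477 per arm) and four looks, power is 90.0%.

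**2. Can the stratum be selected?** Blocks of at most 4 limit the difference to 2 patients per stratum. Maximum ASD = (2/n)/sqrt(p(1−p)), where p is the prevalence of chronic pain (assumed). At n = 477 per arm:

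- p = 0.20: 0.00419/0.400 = 0.010
- p = 0.05: 0.00419/0.218 = 0.019

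Random loss of 10% of patients gives the ASD a standard deviation of about sqrt(2 × 0.1/477) = 0.020, so exceeding 0.10 has a probability of about 1 in a million. In simulation the stratum was selected in 0% of trials.

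**3. How often is surgery type selected?** P(ASD > 0.10) = 2(1 − Φ(0.10/sqrt(2/n))).

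- n = 477 per arm: 0.10/0.0648 = 1.54, giving 12%
- n = 419 per arm: 0.10/0.0691 = 1.45, giving 15%

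**4. Effect on power, type I error and standard error.** The simulation used stratified permuted blocks of 2 and 4, 838 evaluable patients and one final test. It ran 10,000 trials for power (Monte Carlo error about 0.3 points) and 20,000 for type I error (about 0.15 points). Assumed: 20% chronic pain and a 50:50 surgery mix.

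| Share of log variance: surgery / chronic pain | Power: t-test | Power: ASD rule | Power: fixed | Type I: ASD rule | Type I: fixed | Mean SE: ASD rule | Mean SE: fixed |
|---|---|---|---|---|---|---|---|
| 0 / 0 | 90.3% | 90.4% | 90.4% | – | – | – | – |
| 0 / 3% | 89.9% | 89.9% | 90.4% | – | – | – | – |
| 4% / 3% | 90.7% | 91.0% | 92.1% | 4.6% | 5.1% | 0.0685 | 0.0663 |
| 12% / 3% | 90.0% | 91.2% | 94.0% | 4.0% | 4.8% | 0.0681 | 0.0634 |
| 30% / 3% | 90.1% | 92.7% | 97.5% | 3.2% | 5.0% | 0.0670 | 0.0562 |

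The fixed-model standard errors agree with a direct calculation. The unadjusted value is sqrt(4 × 0.9895/838) = 0.0687. Multiplying by sqrt(0.93), sqrt(0.85) and sqrt(0.67) gives 0.0663, 0.0634 and 0.0563.

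**5. Closer to the full plan.** A second simulation used 954 evaluable patients, 20 baseline covariates and four looks at the stated boundaries (4,000 trials per scenario). It assumed 5% of variance from the stratum, 10 to 25% from surgery type and 10% from the other covariates. Overall type I error was 2.9–3.3% under the ASD rule and 4.9–5.1% with a fixed model. The fixed model's standard error was 7–15% smaller.

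**6. Interim looks.** The chance that one unstratified covariate exceeds the threshold is 52%, 36% and 26% at 168, 336 and 504 patients. If the rule is re-applied at each look, one such covariate is in the model at some looks and out at others in 52–63% of trials, depending on look timing.

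**7. Effect of changing only the final model.** This uses the stated boundaries (0.002, 0.005, 0.015, 0.044) and equally spaced looks to 954, with surgery type as the only prognostic factor at 4, 12 or 30%.

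- ASD rule at all four looks: overall type I error 4.9, 4.5, 3.7%
- ASD rule at looks 1–3, fixed model at the end: 5.0, 4.9, 4.8%
- Plain t-test at looks 1–3, fixed model at the end: 5.1, 5.2, 5.5%

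**The case against.** Nothing fails under the current plan. The trial was powered for the t-test, the ASD rule is conservative, and candidates, metric and threshold are all written down and use baseline data only. The size of the loss rests on variance shares that no section supplies, and for the stratum alone it is only about half a point of power. The remedy also alters the primary model after interim looks. If those looks used the plain t-test, overall type I error would rise slightly above 5%. The documents do not show that those who would amend the plan are blind to results by arm: Second interim analysis re-assessment says the executive committee acted on the results of that look, although the reason given is data loss. Finally, surgery type has no defined levels, and making ASD descriptive removes adjustment for other imbalanced covariates.

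Much of this stands. It rules out any claim of an invalid or underpowered analysis, and it sets conditions on how the change is made. It does not remove the point. Adjusting for two factors already recorded costs nothing measurable when they are not prognostic (90.4% against 90.4%) and gains precision when they are. Using 838 patients with a single test rather than 954 with four looks does not drive the result, since both settings start from about 90% power.

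**Conclusion.** The concern holds as a weakness in efficiency and prespecification. Chronic pain is eligible for adjustment on paper but excluded in practice by the blocking. Surgery type is adjusted for in roughly one trial in eight. Type I error stays at or below 5% and the planned 90% power is kept.

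The loss ranges from nothing, if neither factor predicts opioid use, to about 5 points of power and a standard error 16% larger than necessary relative to the ASD-rule value, if surgery type explains 30% of log variance. Prevalence, surgery mix and variance shares are all assumptions. The direction of the effect does not depend on them; its size does. The instability between looks arises only if the rule is re-applied, which the plan leaves open. The change should be made, but the trial does not depend on it.

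**What to change.** Amend G. Statistical Plan and Primary Analysis so that the final primary analysis is a linear regression of log opioid consumption on treatment, chronic pain as used in the randomisation, and surgery type with its levels stated. Report the adjusted ratio of geometric means with its confidence interval. Use the same covariates for the secondary outcomes. Keep ASD as a description of baseline balance, and report the t-test with the ASD rule as a sensitivity analysis, which also shows the effect of any other imbalanced covariate.

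Because interim looks have taken place, the amendment should be dated, made without knowledge of results by arm and before the final unblinded analysis. It should state which model the completed looks used. If they used the ASD rule, the stated boundaries give 4.8–5.0% overall with a fixed final model. If they used the plain t-test, the figure is 5.1–5.5% and the final boundary should be recomputed.

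No new patients or data are needed. The cost is a late, documented change to the primary model and a check of the final boundary.
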